Conditioned Pain Modulation (CPM) : CPM testing involves repeating pressure pain threshold testing in the presence of a heterotopic stimulus (in this case cold water). The testing stimulus will be a mechanical pressure on the left medial knee fat pad. As in the first task, pressure will be applied (0.5 kg/cm²/s ramp) until the participant achieves pressure pain threshold. Baseline pressure pain thresholds of the testing stimulus on the left knee and left shoulder will be determined. After waiting approximately 2 minutes, the conditioning stimulus will be applied by instructing the subject to insert their right hand up to their wrist into a bucket of water maintained between 0-6° C. After 10 s of immersion, subjects will be asked to rate their level of hand pain on a NRS 0-10 scale. After 20s of immersion, the pressure pain threshold will be re-applied using a 0.5 kg/cm²/s ramp rate at the knee and the participant will be asked to rate their knee pain at the time they reached threshold (i.e. pressed the button) on a NRS 0-10 scale. After testing (~20s of immersion), subjects will immediately remove their hand and the pressure pain threshold will be determined at the shoulder. After waiting 5- and 10-minutes after water immersion, the testing stimuli will be re-applied. This paradigm combines a method for measuring CPM⁴⁶ and methods for accurately measuring participation of descending inhibition.⁴⁷ CPM will be measured by the standardized differences in pain threshold, EMG activity and autonomic responses before and after heterotopic stimulation. This strategy will provide the most reliable measurement of descending inhibition.^{47,48}

Temporal Summation (TS): Participants will be instrumented to undergo tests of spinal pain modulation. Temporal summation will be tested using an algometer on the right medial knee fat pad. We will repeatedly apply an amount of pressure (0.5 kg/cm²/s ramp rate; ITI = 5-15 seconds) equal to the average of the participant's two pressure pain thresholds assessed during the first task. After each press, the participant will be asked to rate their pain on an NRS 0-10 scale. The pressure will be applied ten times or until the participant rates their pain as a 6, whichever comes first.

EEG Testing: Subjects will be instrumented with a standard EEG cap. Encephalography (EEG) recordings will be obtained using a standard montage and equipment. A trained research assistant or nurse will place the EEG cap and electrodes. All participants will undergo a resting state EEG task in order to analyze brain activity patterns associated with pain behavior. Participants will be requested to focus on a fixation cross on a computer monitor with their eyes open and sitting with their eyes closed for one minute each. In total, the task is expected to take 10 minutes. All participants will complete a handedness questionnaire,⁴⁹ consisting of a series of questions asking which hand they use for different activities, in REDCap, which will help us interpret our EEG results.

Sensory Amplification Tests: To evaluate whether sensitivity extends to other modalities we will use a software application that measures self-reported unpleasantness to increasingly loud and bright stimuli (safe and well below thresholds that could cause auditory or visual damage).

Auditory stimuli will be provided by waveforms generated by a PC and transmitted through headphones calibrated by an audio monitor⁵⁰. Each stimulus will be a two-tone combination of 1200 and 1350 Hz. Sounds will range in 5 dB steps from 35 to 90 dB SPL (A-weighted). After receiving instructions, the subject will be presented with a series of sounds, in random order of intensity. After each 2 s stimulus, the participant will be asked to rate its unpleasantness from 0 (“not at all unpleasant”) to 20 (“the most unpleasant sound imaginable”).

Visual stimuli will be displayed on a computer monitor capable of providing up to 300 lux. In this 3 min task, two visual stimuli will be presented in an alternating block design. The control stimulus is a fixed crosshair centered in the middle of a solid background; the experimental stimulus will be a flashing (12.5 Hz) blue/yellow checkerboard presented at varying levels of brightness (luminance) in both an ascending and random manner. Each subject will be presented with 6 test patterns alternated with 6 blanks patterns. Subjects will use a 0 (“not at all unpleasant”) to 20 (“the most unpleasant pattern imaginable”) numerical descriptor scale to rate the unpleasantness of each visual stimulus and the entire task.

The visual task may be annoying or elicit a headache or nausea in sensitive individuals. Participants may stop at any time.

The sensory testing will take in total about 20 minutes and will be performed while the participant is connected to EEG.

Additional quality controls: We may need to repeat a task, modify electrode positions, reconfigure equipment, or adjust features in the environment to evaluate the quality of our data acquisition scheme. For example, if a PPT measurement was not obtained or an electrode does not stay put, we may ask the subject to allow us to repeat additional measurements.

All implanted quality controls with permission from the subject will be documented in the subject record.

C1.f Hormone Measurements with Blood (Arm 1 and Arm2): We will ascertain that subjects have not had more than 100 ml of blood drawn over the past 24 hours or 200 ml over the past 30 days. After completion of the pressure/pain testing, a trained nurse or physician will draw up to 60 mL of blood into vacutainers. Separation of serum and plasma will be performed using centrifugation and samples will be aliquoted and banked appropriately to allow for hormone measurements and analyses. To control for the potential influence of reproductive hormones on pain sensitivity, and test our hypothesis about the role of hormonal influences on neurophysiological pain assessments, we will measure serum samples for E2, P4 and testosterone using methods that do not cross-react to the OCs from core laboratories.⁵¹ If the participant gives permission in the consent form, blood samples may also be analyzed for genetics. If the participant gives permission in the consent form, blood samples will continue to be stored after the study is completed for possible future analyses by our lab on women’s health conditions. If the participant does not give permission in the consent form for analyses beyond the current study, their sample will be destroyed upon study completion.

C1.g Follow-up questionnaires: We will ask arm 1 and arm 2 participants to complete an annual follow-up questionnaire including the validated questionnaire instruments mentioned above and a general medical history questionnaire. All arm 1 and arm 2 questionnaires will be

collected electronically using REDCap at home. If requested, paper versions can be provided instead and mailed in. For participants continuing to Phase 2, the year 1 annual medical history questionnaire will usually take place during their assessment #3 visit. All participants that complete phase 1 (Screen + Assessment #1), including phase 2 dropouts, will be asked to complete the annual follow-up questionnaire.

Group (Sample Size)	H (20)	D (20)	D+COS (95)	PBS (40)	P (50)	MSA
Bladder Pain at FU (VAS)	0	0	2.5	3.0	-	0.85
Pelvic Hyperalgesia (VAS)	0	0	3	3	-	0.84
Pelvic Hyperalgesia (Time)	0	0	2	2.5	-	0.83
Pelvic Pain Thresholds	0	.5	.5	2.3	-	0.81
Bodily Pain Thresholds	0	1.5	2	2	2.3	0.91
Conditioned Pain Modulation	0	1-2	1-2	4 _a	2-4 _b	0.94
Menstrual Pain History	0	3.7	5	6	-	0.81
Temporal Summation	0	0	.7	.8	-	-
Estradiol	0	1-3 _c	1-3 _c	1-3	-	0.84
Depression/Anxiety	0	.3	.4	2	2-4	0.82

Table X: Sample sizes and hypothesized results in Z-scores or range of Z-scores (relative to healthy) for subjects that are healthy (H), have dysmenorrhea (D), have cross organ sensitization (D+COS), PBS, or chronic pain (P). MSA indicates Kaiser's measure of sampling adequacy. Numbers in italics indicated minimum detectable hypothesized score with current sample size. Z-scores based on preliminary data, or others indicated by subscript (a: ⁹, b: ^{11,13}). Effects temporal summation in these populations are unknown, but effect sizes as large as 1.1 have been reported for fibromyalgia. Dashes (-) indicate unknown effect size.

C1.h Data Analysis/Sample Size Requirements: The primary outcomes under this hypothesis will be [1] bladder pain at FU, [2] pelvic hyperalgesia (VAS, time to return to baseline pain), reflecting peripheral dysfunction/sensitization, and [3] centrally mediated hyperalgesia (CPM, bodily pain thresholds).

Factor [1], Bladder pain at FU: Our preliminary data on healthy subjects and women with dysmenorrhea, in combination with other studies investigating migraine and PBS, suggests effect sizes between 1.4-5.6 (Cohen's d). As a control comparison, we expect that women with chronic pain will have levels of bladder and pelvic sensitivity comparable to healthy subjects. We will perform t-tests for each of these three pain variables using pairwise contrasts and appropriate Bonferroni corrections for six group comparisons.

Factor [2], pelvic hyperalgesia: To confirm pelvic hyperalgesia (*but not necessarily pelvic PPT*) is higher in those with bladder pain, we will show bladder pain and pelvic hyperalgesia (both VAS and TIME) are higher in D+COS than healthy pain-free controls (H), dysmenorrhea only (D), and chronic pain patients (P). Similarly bladder pain, pelvic hyperalgesia and pelvic floor pain sensitivity (PPT) are anticipated to be greater in PBS than H, and D.

Factor [3], centrally mediated hyperalgesia: Greater central dysfunction manifest by impaired CPM and reduced bodily pain thresholds in vulnerable subjects will be shown by comparing D+COS, PBS, and P to D and H. We estimate 15 subjects per group will provide adequate power (g-power, a priori t-test, $\alpha=0.05$, $\beta=0.2$). To verify we have adequate phenotyping of CPM, we have included the positive control group with chronic pain (P). We assumed the

[figure not shown]
difference in CPM between healthy subjects and chronic pain patients in this protocol would have an effect size of 0.78 based on a meta-analysis (Lewis et al. 2012). Using a 2.6 allocation ratio, a priori power analysis ($\alpha=0.05$, $\beta=0.2$), suggests we need 20 healthy participants and as many as 50 chronic pain patients to detect a difference in the mean CPM. Additionally, the utilization of 50 chronic pain patients will allow us to use regression to identify up to 5 predicted factors associated CPM with correlation coefficients exceeding 0.3 even after correcting for multiple comparisons ($\alpha=0.05$, $\beta=0.2$) as suggested by an a priori random model power analysis. This will be readily captured as our global study design encompasses a larger sample size (Table X) to handle anticipated secondary analysis and projected needs for completion of Phase #2.

Additional confirmatory analysis: Special healthy control subjects (n=10), we will verify special healthy control subjects do not differ from original enrolled healthy control subjects (n=20) to ascertain chronic subjects (P) participating in the trial are not treated differently under blinded conditions.

For the secondary analysis of Phase #1, we will evaluate the D+COS (provoked bladder pain) phenotype while accounting for menstrual history (including historical OC exposure), hormonal factors, anxiety, and depression. To determine the relative contribution of these secondary variables on bladder pain, we will perform principal component analysis (PCA).

We have adequately powered the analysis of these potential covariates consistent with a bootstrap (n=1000 replications, Fig Y) model based on our preliminary data and studies by others (described in Table X). Even with weak correlations ($r=.3$), PCA can detect 3 primary factors with our projected sample size. PCA is an optimal method to identify the mechanisms responsible for bladder pain. Historically PCA with even smaller sample sizes has been employed to measure how coping skills influence pain perception during the menstrual cycle⁵² (n=20) and to show that different pain testing modalities are related to differential psychosocial profiles⁵³ (n=188). Even if PCA fails, we can make many direct comparisons beyond what is described here with t-tests.

Fig Y: Bootstrap simulation constructed assuming a range of correlations between potential mechanisms (e.g. pelvic hyperalgesia and bladder pain) indicate that even with weak correlations we can detect 3 factors. Error bars show 95% confidence intervals.

C1.i Expected outcomes: (1) *Abnormal CPM is the primary predictor of widespread pain sensitivity observed in dysmenorrhea, D+COS and PBS.* Results would be insightful if CPM was worse in participants with D+COS and PBS than those with dysmenorrhea alone because this would indicate CPM mechanisms are involved in COS. On the other hand, if CPM impairments are universal across chronic pain patients, PBS, D, and D+COS compared to healthy controls, this would indicate that pain independent of location and chronicity depends on impaired descending inhibition. This finding would be the basis for developing a physiological biomarker for those at risk of developing CPP/PBS similar to approaches by others identifying risk for chronic pain^{45,79}. On the other hand, some pain conditions such as rheumatoid arthritis¹¹⁴ and trapezius myalgia¹¹⁵ do not seem to exhibit CPM. The vulnerability to conditions unrelated to CPM may involve either inflammatory or specific peripheral nerve events. If CPM does not correlate with widespread pain sensitivity or bladder pain phenotypes in this proposal, we have adequately powered our sample size to detect alternative mechanisms that could be responsible (e.g. menstrual, hormonal, psychological). Nevertheless, consistent with meta-analyses on the menstrual cycle⁵⁴, psychological⁵⁵, and central factors on pain⁵⁶, we anticipate central pain factors to explain the majority of the variance in bladder pain sensitivity. Determining the relative importance of systemic E2 concentrations vs. other modifiable factors such as

menstrual pain will provide insight on the most important mechanisms for reducing bladder pain sensitivity in vulnerable women.

(2) *Pelvic hyperalgesia and severity of menstrual pain are more common in D+COS phenotype vs. dysmenorrhea only.* The identification of clinical biomarkers such as severity of pain after a speculum exam (analogous to the post pelvic floor PPT pain report) can be obtained from our results. Our study results would provide evidence of the significance of this routine clinical exam in reliably predicting bladder sensitivity.

C1.j Potential Problems: *Primary and/or secondary comparisons are nonsignificant: a mixture of mechanisms are involved in D+COS phenotype or PBS.* We will confirm whether our paradigm was sufficient to detect deficits in CPM using our positive control group with chronic pain to validate a true negative finding. Afterwards, we will use cluster analyses to identify phenotype patterns and confirm mechanistic differences with banked serum. *Why not examine additional hormones?* We are examining hormones that have been frequently studied in pain research and will bank serum allowing for the future possibility of studying others. *What about endometriosis, fibroids and other known anatomic uterine pain conditions?* To account for the common conditions (especially within our medical practice), we will include 10 confirmed endometriosis (operative report review) participants and 10 fibroids participants (ultrasound or surgical confirmation) mixed within our dysmenorrhea cohort to determine which effects produced by the primary analysis are due to anatomical conditions.

C2. Methods for Phase #2

C2.a Participation criteria

All phase #1 participants with D+COS (pool of 95 candidates) or PBS (pool of 40) will be enrolled with intent to transition into phase #2, though the second phase of the study will be presented as optional. If they choose not to participate in their randomized group, they will have the option to come back in a year later for an additional assessment visit for long term follow up data. These enrollment targets, accounting for a potential 35% dropout rate, will enroll 62 participants with D+COS and 26 PBS. This will provide adequate power for the prespecified contrasts.

Inclusion Criteria: 1) Participation in Phase #1 and assigned to the Arm #1 PBS or D+COS group, 2) willing to comply with OC assignment (continuous for PBS; cyclical, continuous, or no OC for D+COS).

Exclusion Criteria: a) presence of active pelvic or abdominal malignancies (primary or metastatic), b) absence of regular menses (including current pregnancy, recent pregnancy, or active breast feeding), c) unwilling to undergo pelvic examination/testing, e) standard contraindications to use of OCs:

- Thrombophlebitis or thromboembolic disorders, or a history thereof
- Cerebrovascular or coronary heart disease
- Known or suspected carcinoma of the breast
- Endometrial cancer or other known or suspected estrogen-dependent neoplasia
- Undiagnosed abnormal genital bleeding

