To determine the role of neurophysiological mechanisms in COS, while adjusting for these important covariates, we will characterize a novel phenotype of dysmenorrhea with bladder pain indicative of COS (D+COS). In our preliminary studies, women with the D+COS phenotype exhibited prolonged pelvic pain report in response to a mechanical vaginal stimulus. This hyperalgesia is common among CPP patients. However, in contrast to women with CPP, women with D+COS do not show significant psychological dysfunction. These findings imply dysmenorrhea, independent of psychological factors, influences vulnerability to pelvic pain. Additionally, our preliminary data and work by others show women with dysmenorrhea^{18,19} have widespread reductions in pain thresholds, the hallmark of impaired descending inhibition also observed in IBS.^{20,21} However, specific measures of descending inhibition have never been assessed in women with dysmenorrhea. To address this gap, we propose to conduct cross-sectional and prospective evaluations of pelvic nociception, reproductive hormones and psychological factors among women with dysmenorrhea. In this proposal, we will test the hypothesis that *repeated episodes of menstrual pain increase vulnerability to COS*.

COS may be reversible under ideal circumstances. Hormonal treatment of dysmenorrhea has already been shown to partially alleviate co-morbid irritable bowel syndrome (IBS) and

[figure not shown]

Diagram 1: We hypothesize repeated episodes of menstrual pain could impair descending inhibition of the spinal cord increasing widespread pain sensitivity. Additional local sensitization in the presence of worsening of descending inhibition may result in COS, provoked pelvic pain and bladder hyperalgesia. Elevated concentration of E2 in dysmenorrhea (not shown) could also increase bladder pain.

[figure not shown]
abdominal sensitivity²², and improve painful bladder syndrome (PBS).²³ Our preliminary, cross-sectional data in dysmenorrhea sufferers suggest combined (estrogen and progestin) oral contraceptive (OC) users report less bladder pain at innocuous filling volumes. We would like to investigate further whether this is a modifiable

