phenotype. An equally critical issue involves identifying which patients would respond best to hormonal treatment. Previous studies have yielded conflicting results on whether OCs improve pain modulation.^{24,25} These studies did not address dysmenorrhea or the usage of continuous OCs, which typically ablate withdrawal bleeding and withdrawal bleed-induced uterine nerve activation. *We hypothesize eliminating a painful stimulus with cyclical OCs will improve descending inhibition and reduce COS. (see Diagram 1)*

To determine whether alterations in pain are due to changes in descending inhibition, spinal cord excitability, or peripheral sensitivity we will use established tests for quantitative sensory testing. Changes in descending inhibition will be tested with conditioned pain modulation (**CPM**).²⁶ CPM involves presenting a counter-stimulus (such as cold water) to one part of the body and then simultaneously measuring the differential sensory response to a noxious stimulus elsewhere. The degree of descending inhibition is quantified by comparing the degree of blunted response from a counter-stimulus compared to the unmatched paradigm. Changes in spinal cord excitability will be tested with temporal summation.²⁷ Temporal summation involves evaluating pain report after repetitive stimulation of pain pathway sufficient to induce increased excitability of dorsal horn neurons. Changes in peripheral sensitivity will be evaluated with mechanical pressure testing. We will perform these tests across multiple body sites to determine whether changes in pain mechanisms are regional or body-wide. Performing these tests will allow us to determine whether eliminating a painful stimulus with cyclical OCs improves descending inhibition, spinal excitability, or overall peripheral sensitivity, which will be done in the Phase 2 protocol. The addition of EEG and EMG recordings will also allow us to determine brain and spinal mechanisms that affect nociceptive modulation.

If OCs are shown to improve descending inhibition, our results will extend prior findings in animals that demonstrate descending inhibition is needed to maintain chronic pain states.¹⁰ In humans, descending inhibition is impaired by repetitive pain insults^{28,29} but normalizes with successful interventions.³⁰ Additionally, our results will establish a relationship between descending inhibition and COS allowing for the development of preventative strategies.³¹

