Since endometriosis and fibroids are identifiable anatomical conditions but understanding of their mechanistic contribution to dysmenorrhea and bladder pain is limited, we will include confirmed endometriosis participants and fibroids participants mixed within our dysmenorrhea

cohort to determine which effects produced by the primary analysis are due to anatomical conditions.

Participants are divided into two arms. Arm #1 participants include women ages 18-45 with dysmenorrhea, women with painful bladder syndrome (PBS), and healthy controls. Arm #2 includes women ages 18-45 with chronic pain or special healthy controls.

Our hypotheses on mechanisms responsible for the transition of menstrual pain to bladder pain will be tested through the following phases:

Phase #1 (includes Arm #1 and Arm #2 participants): *To determine if dysmenorrhea with concomitant bladder pain sensitivity exhibits neurophysiological features consistent with established CPP.* Women with dysmenorrhea without COS and women with chronic pain conditions outside of the pelvic region will be used as controls. Quantitative sensory testing (QST) and a noninvasive bladder pain test we previously have validated will be used to determine whether impairments in descending inhibition and pelvic sensitivity are responsible for vulnerability to COS in women with dysmenorrhea (with and without COS) and/or CPP.

Phase #2 (includes a subset of Arm #1 participants only): *To differentiate the individual contributions of circulating sex hormones and repeated sensitizing events (painful menses) on descending and peripheral mechanisms of bladder pain.* The same QST/bladder pain measures studied in Phase #1 will be retested within the D+COS and PBS subjects following a one-year randomized trial of cyclical vs. continuous OCs vs. no treatment. We added a second option for those who are randomized to Phase 2 that did not want to commit to their randomized group. They will be asked to come in for an additional assessment visit a year later. Participating in the randomized group is preferable but this will allow us to still obtain the follow up data that is important with these participants even if they choose not to participate in their assigned group.

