Determining the neurophysiological relationship between repeated uterine inflammation, dysmenorrhea, and COS, and how OCs might reverse that influence, could define a new pathway for understanding the etiology of CPP/PBS. Secondly, identifying early markers of risk could ultimately underlie an effective prevention strategy because the onset of PBS is often gradual with limited symptoms.³²

B. Research Design and Methods

B.1. Overview:

Diagram 2: After screening and washout, dysmenorrhea sufferers with and without COS, PBS patients, and chronic pain participants (with and without pelvic pain conditions) will be compared with controls on experimental pain sensitivity tests (**PPT**), which measure descending inhibition (**CPM**) and pelvic and bladder sensitivity (**Phase #1**). Women with dysmenorrhea with COS and PBS will be asked to participate in Phase #2. In Phase #2, a trial of cyclic and continuous OCs

will be used to differentiate the individual contributions of circulating sex hormones and repeated sensitizing events (painful menstrual periods) on descending and peripheral mechanisms of bladder pain. All participants will also complete a yearly follow-up questionnaire for 5 years (for participants who complete phase 2, the year 1 questionnaire will be incorporated into the 12-month testing Assessment #3 testing session).

This study will enroll a total of approximately 1,080 participants (See **Appendix 1**). Of those subjects, all will be enrolled at NorthShore University HealthSystem (NorthShore). This leaves a total of approximately 1,080 participants to be enrolled in arm #1 (1,020) and arm #2 (60) of the study. We anticipate that some arm 1 and arm 2 participants (up to 415 arm 1 and 10 arm 2 participants) may become ineligible after the screen visit and/or daily diary data because their pain levels do not clearly place them into a defined group, they are enrolled as a dysmenorrhea participant but do not show evidence of COS, medical reasons are identified at the screen visit that were not identified during the phone screen, or they become lost to follow-up between the screen and assessment visit. We expect approximately 645 arm 1 and arm 2 participants will continue the study and complete Phase 1; 515 will be women with dysmenorrhea, 40 will be women with PBS, 40 will be healthy women without pelvic pain or painful periods, 7 will be “special” healthy controls, and 43 will be women with chronic pain.

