Inclusion criteria: Cases: 1) **Dysmenorrhea** cases will have: a) average menstrual pain $\geq 5/10$ (0=no pain and 10=the worst imaginable pain) with menses or withdrawal uterine bleeding from cyclic OCs without painkillers, b) menstrual pain in the region between the umbilicus and the perineum, above the level of the inguinal ligament and c) indication the participant has attempted to resolve pain by medical means (including NSAIDs and/or OCs). Participants who endorse bladder symptoms on the phone screen will be preferentially recruited; those who do not endorse bladder symptoms may be determined ineligible. We found our previous questions to have limited predictive value. Notably because we only want to collect the minimum amount of information necessary to determine eligibility on the phone screen, we may not ask all bladder questions (depending on what future statistics show in regards to what bladder questions accurately predict COS). Participants will complete a daily diary to verify menstrual pain during the screening period.³³ To be eligible as a dysmenorrhea case, a participant must indicate menstrual pain $\geq 5/10$ on at least one day during menses in their daily diary. In the circumstance that a participant originally assigned to the dysmenorrhea group does not reach a pain of 5 on any days on the daily diary, this will be handled on a case-by-case basis particularly if they used a continuous around-the-clock, effective pain treatment regimen. They must have no concurrent chronic pain diagnoses that affect daily life or a history of more than 24 migraines per year. 2) **D+COS participants** will meet criteria for Dysmenorrhea cases, with >15 bladder pain on a 0-100 visual analogue scale (VAS) during either first sensation or first urge at assessment visit #1. Initially participants will be enrolled as dysmenorrhea participants and their final eligibility for D+COS will be determined after their assessment #1 visit. 3) Diagnosis of **PBS participants** will be confirmed by medical records indicating chronic (>3 months) pelvic pain (average intensity $\geq 3/10$), pressure, or discomfort related to the bladder accompanied by at least one other urinary symptom such as persistent urge to void or frequency.³⁴ PBS

participants will also have records review to confirm the exclusion of other conditions by clinical examination or cystoscopy if necessary. PBS participants can have other chronic pain conditions.

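### Phase 1 is to decide what is responsible for vulnerability to COS from measures taken at one visit, and the five years of annual questionnaires enter no listed analysis

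*Combined protocol and SAP*

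**What the plan says.** Section A introduces the two phases with "Our hypotheses on mechanisms responsible for the transition of menstrual pain to bladder pain will be tested through the following phases". The italicised Phase 1 aim is descriptive: whether D+COS looks neurophysiologically like established chronic pelvic pain. The text beneath it goes further and says that the sensory and bladder tests will be used to "determine whether impairments in descending inhibition and pelvic sensitivity are responsible for vulnerability to COS".

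On timing, C1.a sets D+COS by bladder pain above 15 on a 0-100 scale at Assessment Visit #1; for these women, "their final eligibility for D+COS will be determined after their assessment #1 visit". C1.e places the bladder test first at that visit, with pelvic pressure testing and CPM after it.

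On analysis, C1.h plans pairwise t-tests between groups, with Bonferroni correction, and a PCA as the secondary analysis. C1.i would take worse CPM in D+COS and PBS than in dysmenorrhea alone to mean that CPM mechanisms are involved in COS. It would take CPM impairment across all pain groups as the basis for "developing a physiological biomarker for those at risk of developing CPP/PBS".

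On the effect of pain on inhibition, Section A states: "In humans, descending inhibition is impaired by repetitive pain insults".

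On follow-up, B.1 states: "All participants will also complete a yearly follow-up questionnaire for 5 years". C1.g asks this of everyone who completes Phase 1, including Phase 2 dropouts. It consists of the validated questionnaires and a medical history.

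**The concern.** To say that impaired inhibition is responsible for vulnerability to COS is to say that it comes first. The Phase 1 comparison has no time order: the supposed cause and the classification of the outcome come from the same visit. The plan itself supplies the rival explanation, since it holds that repeated pain degrades inhibition. Women who already have bladder or pelvic pain could then show worse CPM because of that pain. The universal impairment that C1.i would build a risk biomarker on is also what that explanation predicts.

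If the plan is followed as written, the report could present a vulnerability or risk conclusion that the test behind it cannot separate from a consequence of pain. Meanwhile, data with the right time order are collected for 5 years with no stated use. An unplanned look at them later would also be hard to read. Only D+COS and PBS women enter Phase 2, so a comparison by baseline group would mix natural history with OC treatment.

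**Working it through.** **1. The plan's own CPM figure.** C1.h sizes healthy versus chronic pain at d = 0.78, allocation 2.6, alpha 0.05 and power 0.80, and states 20 and up to 50. With a two-sided two-sample t-test, noncentrality = d × sqrt(n1·n2/(n1+n2)). For 20 and 50 this is 0.78 × sqrt(1000/70) = 2.95, which gives power 0.83. The smallest design reaching 0.80 is 19 and 50 (power 0.81). The stated figure reproduces. It concerns detecting a difference and says nothing about direction.

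**2. Can the contrast show direction?** Illustration with an assumed correlation of 0.35 between CPM impairment and bladder pain (both standardised), split in Table X's ratio of 20 D to 95 D+COS.

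- Share below the cut: p = 20/115 = 0.174, so z = -0.94 and the normal density there is 0.257.
- Mean bladder-pain difference between the two groups: 0.257/0.826 + 0.257/0.174 = 1.79 SD.
- CPM difference: 0.35 × 1.79 = 0.626.
- Within-group SD: sqrt(1 - 0.174 × 0.826 × 0.626²) = 0.97.
- d = 0.626/0.97 = 0.64.

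Only the correlation enters this calculation, not the arrow behind it. Simulation gives the same answer for each structure:

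| Structure | d | Power, 20 vs 95, two-sided 0.05 |
|---|---|---|
| Impaired inhibition leads to bladder pain | 0.64 | 0.74 |
| Bladder pain leads to impaired inhibition | 0.65 | 0.74 |
| Common cause | 0.64 | 0.73 |

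The differences are simulation noise. A common cause is not far-fetched: Table X itself projects more menstrual pain history in D+COS (5) than in D (3.7), and the same CPM range (1-2) in both.

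**3. Which analyses use the annual data?** C1.h names no follow-up outcome. In C2.h, Z1 to Z5 stop at 6 and 12 months. For Phase 2 completers the year-1 questionnaire is folded into the 12-month visit, but none of Z1 to Z5 names it.

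**4. What could a prospective analysis deliver?** Illustration only: baseline CPM compared between women who do and do not later report new bladder or pelvic pain, two-sided t-test at 0.05. Assumed incidence is 5-20% and assumed retention 65-100%. The d of 0.78 is borrowed from step 1.

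| Non-COS dysmenorrhea women | Later cases | Power at d = 0.78 | Power at d = 0.5 |
|---|---|---|---|
| 20 (Table X) | 1-4 | at most 0.26 | at most 0.14 |
| 420 (515 - 95, assumed) | 14-84 | 0.81 to >0.99 | 0.44 to 0.98 |

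The documents do not state how many non-COS dysmenorrhea women will complete Phase 1. These figures are not the power of the mixed model proposed below.

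**The case against.** The strongest reply is that the wording is loose but the design is not. The headline Phase 1 aim is descriptive and a cross-sectional contrast can answer it. C1.i says only that CPM mechanisms would be involved in COS, the chronic pain group helps separate general pain from COS, and the biomarker is something to develop later. Phase 2 then randomizes D+COS women and retests bladder pain and CPM. All of this is fair. It limits the point to the vulnerability and risk wording, but it does not rescue that wording. A chronic pain comparator does not settle direction. Phase 2 enrols only women who already have COS or PBS, does not randomize PBS, and in Z5 compares improvers with non-improvers, which is not a randomized contrast.

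Three stronger readings are tempting and unsupported:

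- A reader might infer that Diagram 1 contradicts the Phase 1 aim. It does not. Its caption, "We hypothesize repeated episodes of menstrual pain could impair descending inhibition of the spinal cord", begins one chain in which menstrual pain impairs inhibition and this, with local sensitization, leads to COS. The rival path rests on Section A's general statement about repetitive pain.
- A reader might infer that the annual follow-ups could establish direction. They repeat neither CPM nor the bladder test, so they cannot detect new COS, and confounding would remain.
- A reader might infer that the hypotheses go untested altogether. Phase 2 does test reversal.

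The public version is edited and refers to sections that are not in it, so a use for the annual data may be described elsewhere. The statement here covers only the analyses listed in C1.h and C2.h.

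**Conclusion.** The point holds in a limited form. The Phase 1 contrasts and PCA can show that CPM and pelvic sensitivity are associated with D+COS and PBS. They cannot show that impairment is responsible for vulnerability or marks future risk, and a larger sample does not change this. That follows from the visit schedule and the plan's own statement about repetitive pain; the correlation of 0.35 only illustrates it.

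The annual questionnaires are the only data on all Phase 1 completers in which symptoms follow the CPM measurement, and no listed analysis uses them. Their value is time order for later symptoms. How much they can show ranges from very little (20 non-COS dysmenorrhea women) to useful (about 420), and the second figure assumes that 515 dysmenorrhea women complete Phase 1 and only 95 of them have COS. The one-in-five progression to chronic pelvic pain in Section A has no time frame, so it does not fix an event rate for the 5 years. The data collected remain sound; the stated conclusions and one missing analysis need attention.

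**What to change.** 1. In Section A, C1.h and C1.i, word the Phase 1 CPM and pelvic conclusions as association. Do the same for the risk and biomarker reading of a universal CPM impairment.

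2. Prespecify one prospective analysis of the annual questionnaires:
   - Outcome: Genitourinary Pain Index or Interstitial Cystitis Index pain score over years 1 to 5, with one named as primary.
   - Model: mixed model adjusted for the baseline score, stating whether this is the screening or the Assessment #1 value.
   - Predictors: Assessment #1 CPM, bladder VAS as a continuous score, and menstrual pain.
   - Main population: dysmenorrhea and healthy women without PBS and without COS at Assessment #1.
   - D+COS women: a separate analysis of worsening, since they already have the condition whose onset is in question.
   - Treatment: terms for OC use, and for Phase 2 assignment where it applies (the D+COS analysis). The annual medical history would need to capture OC use.
   - Missing questionnaires: a stated method, with return rates by group and year.

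3. State with the model that it gives time order for later symptoms, not new COS and not freedom from confounding. State too how many non-COS dysmenorrhea women it is expected to include.

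The cost is wording and one added model on data already being collected, with no new visits. The downside is that results come later and depend on questionnaire return.
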